6.3 MEASURES TO MINIMIZE BIAS: RANDOMIZATION AND MASKING

Allocation to study treatment will occur in a double-masked manner on 2 occasions: **initial randomization** at Baseline (for Primary Treatment Period [Part 1]) and **re-randomization** at Month 36 (for Randomized Withdrawal Period [Part 2]).

For Part 1, prior to initiation of study treatment, randomization will occur by site staff via the IVRS/IWRS once it is confirmed that the participant meets the final study entry criteria (see [Sections 5.1](#) and [5.2](#)). The IVRS/IWRS will provide the participant identification number used on all study documents and will be used to manage the randomization and treatment assignment based on a stratified randomization scheme prepared by Sydnexis' designee. Initial randomization will be in a 1:1:1 ratio of SYD-101 0.01%: SYD-101 0.03%: Vehicle and stratified by baseline SE (0.50 D to 3.0 D and >3.0 D to 6.0 D) and age (3 years to <6 years, 6 years to <9 years, 9 years to <12 years, and 12 years to 14 years).

To maintain treatment masking for Part 2, sites will contact the IVRS/IWRS at Month 36 for all participants. At Month 36, participants who were initially assigned (at Baseline) to SYD-101 0.01% will be re-randomized in a 1:1 ratio to masked SYD-101 0.01% or Vehicle; participants initially assigned (at Baseline) to SYD-101 0.03% will be re-randomized in a 1:1 ratio to masked SYD-101 0.03% or Vehicle. The Re-randomization of SYD-101 participants will not be stratified. All participants who were initially assigned (at Baseline) to Vehicle will be re-randomized to masked SYD-101 0.03% at Month 36.

Sites will also contact the IVRS/IWRS at the time a participant qualifies to initiate treatment with escape medication (ie, at confirmatory visit when measurements confirm progression of myopia ≥ 2.00 D in SE from baseline) for ANY participant who has qualified for and desires to use escape medication.

Study drug will be labeled with medication kit numbers, and the IVRS/IWRS will provide each site with the specific medication kit number(s) for each randomized participant at the time of

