MAR imputations will be performed separately for each treatment arm and the imputation model will include terms for age at baseline, baseline SE (average of both eyes), and SE values (average of both eyes) for each post baseline scheduled visit through the specified analysis timepoint, Month 24 or Month 36 as applicable.

Imputations for data assumed to be MNAR will be first imputed via MCMC multichain methods to obtain monotone data as above for MAR imputations. The remaining missing SE values will be imputed via a sequential vehicle-based pattern imputation using regression methods (Ratitch, 2011) for the scheduled SE visits through the analysis timepoint, Month 24 or Month 36, using a model including age at baseline and baseline SE (average of both eyes) followed by sequential visits through M24 or M36, imputed values for those on SYD-101 treatment will be based on the Vehicle group.

EMA Submission:

The annual progression rate of myopia for a given timepoint will be calculated as the negative change in SE (average of both eyes) from baseline, divided by the number of days to the timepoint (visit date – date of first dose of study drug + 1), and multiplied by 365.25 days/year. The average of SE for the right and left eyes will be used for analysis.

SYD-101 0.01% and SYD-101 0.03% will be compared to Vehicle for the annual progression rate of myopia after 24 months of treatment using a REML-based MMRM model including fixed effects for treatment group, baseline age category, categorical visit, and the treatment group by visit interaction, with baseline SE value (average of both eyes) as a covariate. An appropriate covariance structure will be selected, and the Kenward-Roger Method will be used to calculate the denominator degrees of freedom for the test of fixed effects. All visits through Month 24 will be included in the model, with the primary comparison at the Month 24 visit.

The MMRM model will be repeated for each imputation and the results combined via SAS PROC MIANALYZE for final treatment estimates. The mean annual progression rate of myopia for each treatment and the estimated mean difference between each SYD-101 treatment group and Vehicle will be presented along with their corresponding 95% CIs.

The analysis of the primary endpoint will be based on the FAS. As a sensitivity analysis, an analysis will be repeated for the Per-Protocol Analysis Set and using other imputation approaches for the FAS.

US FDA Submission:

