For the EMA submission, the fast progressors subset analyses of the mean annual progression rate of myopia using data through Month 24. The analysis will use the same methodology as specified for this endpoint in [Section 9.4.2](#) as for the EMA primary efficacy endpoint, however data after receipt of prohibited treatment or escape medication will be censored and multiple imputation will not be performed for this endpoint.

The mean change from baseline in axial length will be analyzed similarly to the annual progression rate of myopia as detailed in [Section 9.4.2](#) for the primary EMA analysis, however multiple imputation will not be performed and analysis of axial length will be performed on observed data only.

The testing procedure for multiple secondary endpoints is described in [Section 9.1](#).

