SYD-101 0.01% and SYD-101 0.03% will be compared to Vehicle for the annual progression rate of myopia after 24 months of treatment using a REML-based MMRM model including fixed effects for treatment group, baseline age category, categorical visit, and the treatment group by visit interaction, with baseline SE value as a covariate. No explicit structure will be assumed for the covariance among the repeated measures. However, in case there is a convergence problem with the unstructured covariance, then a compound symmetry covariance structure will be assumed. The Kenward-Roger Method will be used to calculate the denominator degrees of freedom for the test of fixed effects. All visits for the Month 24 analysis will be included in the model, with the primary comparison at the Month 24 visit.

The above model will be performed for each imputation and the results combined via SAS PROC MIANALYZE for final treatment estimates. The estimated mean annual progression rate of myopia for each treatment at each visit and the estimated mean difference between each SYD-101 treatment group and Vehicle at Month 24 will be presented along with their corresponding 95% CIs.

The analysis described above will be performed for annual progression rate of myopia by eye at Month 24 and repeated for the annual progression rate of myopia at Month 36 with the MMRM model including data for visits through Month 36 as a secondary analysis.

FDA Submission: Confirmed Progression > 0.75 D

Progression is defined as an increased negative change where change is calculated as visit value – baseline value. Progression will be considered missing if a valid SE measurement is not available for both eyes at the given visit. The multiply imputed SE data will be used to determine confirmed progression. For analyses, progression will be considered confirmed if at the next consecutive visit, regardless of the number of days from the prior visit, progression >0.75 D continues to be demonstrated.

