The proportion of participants with confirmed myopia progression (>0.75 D) at Month 36 will be compared between each dose of SYD-101 and Vehicle using pairwise CMH tests to account for randomization factors (ie, baseline SE and age categories). The pairwise CMH tests will be performed and the Mantel-Haenszel common risk difference 95% CIs will be calculated for each of the k imputed datasets and the results combined via SAS PROC MIANALYZE for final treatment estimates. Point estimates and CIs will be presented in summary tables as percentages (i.e., the estimated proportions * 100).

Rubin's pooling methodology utilized in SAS PROC MIANALYZE is based on assumption that the estimates are asymptotically normally distributed. The CMH test follows a Chi-Square distribution which is highly skewed for smaller degrees of freedom and can violate Rubin's assumptions. Prior to combination of data in the MIANALYZE procedure, the individual CMH test statistics will be transformed to an approximate Normal (0,1) variables using the Wilson-Hilferty transformation ([Wilson & Hilferty, 1931](#); [Goria, 1992](#)).

The number and percentage of participants in each treatment group who meet the definition of myopic progression will be presented. These values will be based on the averages from the k imputations.

The same analysis will also be performed at Month 24 looking at progression at or before Month 24 as a secondary analysis.

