The mean change from baseline in axial length will be analyzed similar to the annual progression rate using a REML-based MMRM model including fixed effects for treatment group, baseline age category, categorical visit, and the treatment group by visit interaction, with baseline axial length as a covariate. No explicit structure will be assumed for the covariance among the repeated measures. However, in case there is a convergence problem with the unstructured covariance, then a compound symmetry covariance structure will be assumed. The Kenward-Roger Method will be used to calculate the denominator degrees of freedom for the test of fixed effects. For analysis at Month 24, all through Month 24 will be included in the model. Observations after receipt of prohibited treatment or escape therapy will be censored. Observations after treatment discontinuation will be included as observed. Multiple imputation will not be performed. A single average axial length for the right and left eyes will be used for analysis.

Proportionate progression rate endpoints using different cutoffs to define myopic progression (eg, ≤ 0.25 D/year, ≤ 0.50 D/year, and an increase of myopia of 0.50 D) will be analyzed similar to the primary endpoint using pairwise CMH tests; however, sensitivity analyses, other than PPS analyses, will not be performed.

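### Free improvement: add baseline spherical equivalent, a randomization stratum, to the axial-length model and record the covariate choice

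*SAP*

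**What the plan says.** In this note SE means spherical equivalent; standard error is written out.

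Protocol 6.3 has the initial randomization "stratified by baseline SE (0.50 D to 3.0 D and >3.0 D to 6.0 D) and age", with four age bands. SAP 3.1 and 4.2 repeat this.

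For axial length, SAP 8.2 specifies a REML-based mixed model for repeated measures with "fixed effects for treatment group, baseline age category, categorical visit, and the treatment group by visit interaction", and "with baseline axial length as a covariate". Baseline SE does not appear. Observed data only are used, without multiple imputation.

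The protocol has no covariate list of its own for this endpoint. Protocol 9.4.3 says: "The mean change from baseline in axial length will be analyzed similarly to the annual progression rate of myopia", and points to 9.4.2. The model there is fitted "with baseline SE value (average of both eyes) as a covariate"; the SAP version of the rate model (8.1.1) is likewise fitted "with baseline SE value as a covariate".

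The other tested efficacy analyses take both randomization factors into account. The CMH tests in SAP 8.1.1 adjust for baseline SE and age categories, the log-rank test in SAP 8.2 is stratified by the randomization factors, and the fast-progressor analyses follow the rate model (Protocol 9.4.3). SAP Section 11, which lists changes to the planned analysis, does not mention the covariates of the axial-length model.

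**The concern.** A model fitted after stratified randomization normally carries the stratification factors. Here one of the two is absent from a single tested endpoint, and no reason is given. If baseline SE predicts axial growth beyond what age and baseline axial length already explain, leaving it out costs some precision.

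Axial length is formally tested in both hierarchies and is measured only at sites with the equipment. If only one dose has survived the earlier steps, it is tested at 0.005 (SAP 8.2). A small, free gain in precision is therefore worth having. The importance is limited, because axial length comes last in both hierarchies (secondary endpoint 8 for EMA and 6 for FDA in SAP Table 3-3) and the documents set no power target for it.

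**Working it through.** **The plan's own figure.** The documents give no power, SD or effect for axial length. The nearest stated figure is for the progression rate (SAP 4.1): 280 per arm, difference 0.18 D, SD 0.60 D, two-sided 0.025, power above 90%. The standard error is 0.60 × √(2/280) = 0.0507, and 0.18/0.0507 = 3.55. Subtracting the critical value 2.24 leaves 1.31, so power is about 90.5% (90.3% with the t distribution). The figure reproduces, but it does not bear on axial length.

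**Size of the gain.** Let R² be the share of residual variance that baseline SE explains after age and baseline axial length. Adding it multiplies the standard error by √(1 − R²), and the equivalent saving in sample size is R². The documents give no R²; the range below is assumed.

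| Assumed R² | Factor √(1 − R²) | Fall in standard error | Children, if 420 measured | Children, if 210 measured |
|---|---|---|---|---|
| 1% | 0.995 | 0.5% | 4.2 | 2.1 |
| 2% | 0.990 | 1.0% | 8.4 | 4.2 |
| 5% | 0.975 | 2.5% | 21 | 10.5 |

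The two sample sizes are 50% and 25% of 840. SAP Table 3-3 says at least 50% of participants; footnote m of the SAP schedule of events (14.2) says approximately 25%.

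**Validity of the planned model.** This was simulated as a single-visit analysis of covariance with 140 children per arm, stratified in permuted blocks of 6 within the 2 × 4 strata, residual SD 1, and 3,000 runs per setting. Block size, age mix, the correlation of axial length with SE (0.3, 0.6 or 0.8) and the slope on standardized SE (0 to 0.60) are assumptions. With no treatment effect, the SAP model gave:

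- absolute bias below 0.005;
- model standard error divided by the true SD of the estimate: 0.98 to 1.05;
- rejection at nominal 0.05: 0.038 to 0.058, with Monte Carlo error of about 0.008.

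Only at slope 0.60, an extreme case, was the model standard error clearly too large (about 3% to 5%; rejection 0.038 to 0.044).

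**Power, same set-up.** Correlation 0.6, effect 0.38 residual SD, two-sided 0.025. Here R² = b²(1 − 0.6²)/(1 + b²(1 − 0.6²)) for slope b.

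| Slope b | R² | SAP model | With baseline SE |
|---|---|---|---|
| 0.15 | 0.0144/1.0144 = 1.4% | 81.5% | 82.0% |
| 0.30 | 0.0576/1.0576 = 5.4% | 80.6% | 82.4% |
| 0.60 | 0.2304/1.2304 = 18.7% | 72.9% | 81.5% |

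The first two rows roughly match the assumed 1% to 5% and show a gain of 0.5 to 1.8 percentage points. The third lies far outside that range.

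**The axial-length subset.** The runs above treat the measured children as stratified among themselves. In the trial they are a subset defined by site equipment, and site is not a stratification factor. When 840 children were stratified and a random half kept (correlation 0.6, slopes 0.15 to 0.60), the ratio of model standard error to true SD was 0.99 to 1.00 and null rejection 0.046 to 0.052. In that setting the planned standard error is about right, and adding baseline SE is a pure gain in efficiency.

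**The case against.** The strongest reply is that the planned model is already the natural analogue of the rate model. The rate model adjusts for the baseline of its own outcome, SE; the axial-length model adjusts for the baseline of its own outcome, axial length. The protocol's wording leaves room for that. Age category, the factor with four levels, stays in the model, and baseline axial length probably carries part of the information in baseline SE. The model is prespecified and valid, and the endpoint is last in line. All of this stands, and it limits the point to an improvement.

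A reader might go further and infer that the standard error ignores the stratified design, or that type I error is at risk. The documents do not support that: one of the two strata is in the model, and omitting the other can only make the test conservative. A reader might also infer that the planned standard error is demonstrably too large by the percentages in the first table. Those percentages compare two models under an assumed R²; they do not measure an error in the planned one, and because the subset is only partly balanced on SE by design, even the direction of any miscalibration is weak.

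What the reply leaves unanswered is why this one tested analysis lacks baseline SE, and why the choice is not recorded.

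**Conclusion.** The point holds as a free improvement. The axial-length model is the only tested efficacy analysis that does not account for baseline SE, and the choice is undocumented. It is not a contradiction between protocol and SAP, and it threatens no conclusion.

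The likely gain is a standard error 0.5% to 2.5% smaller, conditional on baseline SE explaining a further 1% to 5% of residual variance. The true value could be nearer zero if baseline axial length already carries most of that information. The simulations use one visit and complete data rather than the full repeated-measures model.

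The conflict over the size of the subset matters far more for precision. With 70 instead of 140 children per arm, the standard error is √(140/70) = 1.41 times as large, or about 41% larger.

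**What to change.** In SAP 8.2, keep baseline axial length and age category in the axial-length model and add baseline SE (average of both eyes, as in the rate model), for the Month 24 and the Month 36 analyses. Record the covariate choice and its reason in SAP Section 11 before unmasking. The cost is one model term and one degree of freedom, with no new data, because baseline SE is collected on every child. If it turns out not to be prognostic, the loss is negligible: in the simulation with slope zero and correlation 0.3, the standard error went from 0.1195 to 0.1196.

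In the same revision, reconcile the share of participants with axial length between SAP Table 3-3 and footnote m of the SAP schedule of events.

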8.3. Other Efficacy Endpoints

Data collected after Month 36 will be considered exploratory analysis and summarized separately using descriptive statistics only and based on observed data. Participants will be grouped by treatment pathway from the start of study through the re-randomization (original SYD-101 0.01% and SYD-101 0.03% participants) and transition to active treatment (original Vehicle participants) at Month 36:

- Participants initially randomized to SYD-101 0.01% at Baseline and re-randomized to SYD-101 0.01% at Month 36
- Participants initially randomized to SYD-101 0.01% at Baseline and re-randomized to Vehicle at Month 36
- Participants initially randomized to SYD-101 0.03% at Baseline and re-randomized to SYD-101 0.03% at Month 36
- Participants initially randomized to SYD-101 0.03% at Baseline and re-randomized to Vehicle at Month 36

- Participants initially randomized to Vehicle at Baseline and re-assigned to SYD-101 0.03% at Month 36

In general, data collected after Month 36 will be summarized according to the above groupings. As applicable, the groupings above may be further refined based on receipt of escape medication after Month 36. Changes in continuous measures will be relative to the data collection at the Month 36 visit, unless otherwise specified.

Summaries to be provided for the grouping above include:

- Mean change from Month 36 in SE
- Mean annual progression rate from Month 36 to Month 48
- Proportion of participants with myopic progression from Month 36 >0.75 D
- Proportion of participants with annual myopia progression rate from baseline to Month 48 ≤ 0.50 D/year
- Proportion of participants with annual myopia progression rate from baseline to Month 48 ≤ 0.25 D/year
- Proportion of participants with increase from baseline of myopia of >0.50 D at Month 48
- Mean change in axial length from Month 36 to Month 48

To evaluate the potential rebound effect once participants discontinue SYD-101 therapy, exploratory analyses will be conducted on the set of participants initially randomized to SYD-101 (0.01% or 0.03%) at Baseline and who are re-randomized to Vehicle at Month 36. The mean annual progression rate from baseline to Month 36 will be numerically compared to the mean annual progression rate from Month 36 to Month 48 within this set of participants. For comparison, the same summaries will be presented for participants randomized SYD-101 therapy and who are not re-randomized to Vehicle at Month 36. Summary statistics will be presented by initial randomization group.

To evaluate the potential rebound and re-treatment effect once participants discontinue SYD-101 therapy, exploratory analyses will be conducted on the set of participants initially randomized to SYD-101 (0.01% or 0.03%) at Baseline and who are re-randomized to Vehicle at Month 36. The mean annual progression rate from Baseline to Month 36 will be numerically compared to the mean annual progression rate from Month 36 to Month 48 within this set of participants to investigate rebound. For comparison, the time intervals will be summarized for participants randomized SYD-101 therapy and who are not re-randomized to Vehicle at Month 36. Additionally, these summaries will also be subset by receipt of escape medication after Month 36.

To evaluate the escape medication effect, select summaries and plots will be provided by numerically comparing the participants who never received escape medication and the participants who received escape medication at Month 24, Month 30 and Month 36 by initial randomization group. Summaries and plots will be presented from Baseline to Month 36, and will include:

- Mean change from baseline in SE
- Mean annual progression rate

- Mean change from baseline in axial length

Select summaries will be provided for the subset of participants initially randomized to SYD-101 (0.01% or 0.03%) at Day 1 (Baseline) and re-randomized to SYD-101 at Month 36 and who remain on SYD-101 for the entire duration of the study. This will be done to characterize the efficacy profile of those participants receiving up to 48 months of SYD-101 treatment. Summaries to be presented for this subset of participants includes:

- Mean change from baseline in SE
- Mean annual progression rate from baseline to Month 48
- Proportion of participants with myopic progression >0.75 D at or before Month 48
- Proportion of participants with annual myopia progression rate from baseline to Month 48 ≤ 0.50 D/year
- Proportion of participants with annual myopia progression rate from baseline to Month 48 ≤ 0.25 D/year
- Proportion of participants with increase from baseline of myopia of >0.50 D at Month 48
- Mean change from baseline in axial length at Month 48

Time spent on various activities (e.g., time spent on near activities, time spent outdoors, etc.) will be descriptively summarized by timepoint for each treatment group.

Time on activities will be collected separately for school/workdays. For analysis, the average hours per day for the week will be calculated as $(5 \times \text{school/workday value} + 2 \times \text{weekend value}) / 7$. Responses of “none” will be considered 0 hours and responses of “3 or more hours” will be included as 3 hours. The mean and 95% confidence intervals for time on activities by treatment, visit and subgroups defined in Section 8.1.3 will be provided if applicable.

As noted in Section 8.1.3 proportion of participants with myopic progression and the mean annual progression rate will be summarized numerically by subgroups defined by the time spent on various activities. For each type of activity, time outdoors and near work, the weekly average responses will be averaged to calculate an overall average per participant, and the median of the per participant overall averaged responses will be used to define the subgroups.

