For participants with measured myopia progression ≥ 2.00 D from baseline in SE at a visit occurring between Month 18 and Month 36 (inclusive), and measurements obtained 6 months later at the next scheduled visit confirm myopia progression (ie, confirmation at a visit between Month 24 and Month 42 [inclusive]), then treatment with **escape medication** (active SYD-101 0.03%) may be initiated at the confirmatory visit and continued until Month 48. Participants on escape medication will adhere to the same visit schedule. No medications will be dispensed during or after the Month 48/End of Study (EOS) visit.

Clinic visits (with an investigator) will be at Screening, Baseline (Day 1), Month 3, Month 6, and every 6 months thereafter until Month 48 or Early Termination (ET). A telephone visit with the study coordinator will occur at Week 2 and between clinic visits, from Months 9 through 39.

Specular microscopy will be done so that approximately 25% of participants will have an assessment for endothelial cell counts at sites with the requisite equipment. Axial length will be measured at sites with the requisite equipment (at least 50% of study participants).

There are 3 planned database locks for this study. The first will occur after all participants have completed the Month 24 visit for the purpose of submitting data for regulatory submission to the EU (ie, Month 24 analysis). The second database lock will occur after all participants have completed the Month 36 visit for regulatory submission to the US (ie, Month 36 analysis). The final database lock will occur after all participants have completed the last study visit (Month 48 or ET) to allow assessment of the persistence of effect of SYD-101 after 12 months of randomized withdrawal (ie, Month 48/Final analysis). Details regarding efficacy analyses are provided in [Section 9.4.2](#).

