9.4.9 EXPLORATORY ANALYSES

Data collected after Month 36 will be considered exploratory analysis and summarized separately using descriptive statistics. Participants will be grouped by treatment pathway from the start of study through the re-randomization (original SYD-101 0.01% and SYD-101 0.03% participants) and transition to active treatment (original Vehicle participants) at Month 36:

- Participants initially randomized to SYD-101 0.01% at Baseline and re-randomized to SYD-101 0.01% at Month 36
- Participants initially randomized to SYD-101 0.01% at Baseline and re-randomized to Vehicle at Month 36
- Participants initially randomized to SYD-101 0.03% at Baseline and re-randomized to SYD-101 0.03% at Month 36

- Participants initially randomized to SYD-101 0.03% at Baseline and re-randomized to Vehicle at Month 36
- Participants initially randomized to Vehicle at Baseline and re-randomized to SYD-101 0.03% at Month 36

In general, data collected after Month 36 will be summarized according to the above groupings. As applicable, the groupings above may be further refined based on receipt of escape medication between Month 24 and Month 42 (inclusive). Changes in continuous measures will be relative to the data collection at the Month 36 visit, unless otherwise specified. Adverse events will be summarized separately for those events with onset after Month 36.

To evaluate the potential rebound effect once participants discontinue SYD-101 therapy, exploratory analyses will be conducted on the set of participants initially randomized to SYD-101 (0.01% or 0.03%) at Baseline who are re-randomized to Vehicle at Month 36. The mean annual progression rate from baseline to Month 36 will be numerically compared to the mean annual progression rate from Month 36 to Month 48 within this set of participants.

Select summaries will be provided for the group of participants initially randomized to SYD-101 (0.01% or 0.03%) at Day 1 (Baseline) and re-randomized to SYD-101 at Month 36 and who remain on SYD-101 for the entire duration of the study. This will be done to characterize the safety and efficacy profile of those participants receiving up to 48 months of SYD-101 treatment.

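### The rebound analysis rests on a within-group before/after comparison, and the randomized Vehicle-minus-continued difference for Months 36 to 48 is never estimated

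*SAP*

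**What the plan says.** At Month 36 each active arm is re-randomized 1:1 to continue its dose or switch to Vehicle (Protocol 4.1 and 6.3; SAP 4.2). Protocol 4.1 gives the purpose of the final database lock as "assessment of the persistence of effect of SYD-101 after 12 months of randomized withdrawal".

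For rebound, Protocol 9.4.9 states that "exploratory analyses will be conducted on the set of participants initially randomized to SYD-101 (0.01% or 0.03%) at Baseline who are re-randomized to Vehicle". Their baseline-to-Month 36 rate is set numerically against their own later rate. SAP 8.3 repeats this: the earlier rate "will be numerically compared to the mean annual progression rate from Month 36 to Month 48 within this set of participants". The SAP then adds a side-by-side group: "For comparison, the same summaries will be presented for participants randomized SYD-101 therapy and who are not re-randomized to Vehicle at Month 36". It also says: "Summary statistics will be presented by initial randomization group". Its second rebound paragraph repeats the comparator ("For comparison, the time intervals will be summarized for participants randomized SYD-101 therapy and who are not re-randomized to Vehicle at Month 36") and adds a split by escape use after Month 36.

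SAP 8.3 also tabulates several outcomes for all five treatment pathways, including "Mean annual progression rate from Month 36 to Month 48". All data after Month 36 are to be "summarized separately using descriptive statistics only and based on observed data". Neither document names a between-group difference, a confidence interval, a model or a definition of rebound for this period.

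**The concern.** Part 2 randomizes withdrawal, so children continued and withdrawn on the same dose can be compared at the same age and calendar time. The named rebound comparison instead sets each withdrawn group against its own past. Any change in progression that comes with age then enters the result. The SAP Introduction says myopia usually stabilizes around puberty, and children who enter at 3 to 14 years are about 6 to 17 at Month 36. Ageing therefore pulls the later rate down while loss of drug effect and any rebound push it up, and the before/after figure reports only the net.

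At stake is how the withdrawal period is read, since rebound after stopping atropine is a safety and labelling question that the Protocol raises itself (2.1.2, 2.3.1 and the exploratory endpoint in Section 3).

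**Working it through.** **Planning figures.** The documents give no precision figure for the rebound analysis. The nearest stated figure is power above 90% for a 0.18 D/yr difference, with SD 0.60, 280 per arm and two-sided alpha 0.025 (Protocol 9.2; SAP 4.1). It reproduces: 0.18 / (0.60 × √(2/280)) = 3.55; 3.55 − 2.24 = 1.31; power 90.5% (90.3% with the noncentral t).

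**Inputs.** SAP 4.1 assumes 0.65 D/yr on Vehicle, 0.325 D/yr on active drug, SD 0.55 and 7% annual dropout or treatment discontinuation. The rate of slowing with age is not given; 10-20% a year is assumed.

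**Time gap.** Baseline to Month 36 is centred on Month 18, and Month 36 to 48 on Month 42. The gap is 24 months.

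**Effect of ageing on the untreated rate.** 0.65 × (1 − 0.9²) = 0.124 D/yr; 0.65 × (1 − 0.8²) = 0.234 D/yr.

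**What each comparison would show.** The earlier treated rate is 0.325. At Month 42 the untreated rate is 0.65 × k and the treated rate 0.325 × k, where k = 1, 0.81 or 0.64 (the drug effect is assumed to stay at 50%). Rebound means an excess over the untreated rate at that age; 0.10 D/yr is illustrative.

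| Slowing per year | Before/after, no rebound | Before/after, rebound 0.10 | Vehicle minus continued, no rebound | Vehicle minus continued, rebound 0.10 |
|---|---|---|---|---|
| 0% | 0.325 | 0.425 | 0.325 | 0.425 |
| 10% | 0.202 | 0.302 | 0.263 | 0.363 |
| 20% | 0.091 | 0.191 | 0.208 | 0.308 |

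Example, 20% with no rebound: 0.65 × 0.64 − 0.325 = 0.091 before/after; 0.65 × 0.64 − 0.325 × 0.64 = 0.208 between groups.

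A rebound of 0.10 with 20% slowing (0.191) gives a smaller before/after rise than no rebound with 10% slowing (0.202). Against the concurrent withdrawal effect, the before/after change falls short by 0.263 − 0.202 ≈ 0.06 to 0.208 − 0.091 ≈ 0.12 D/yr. With no rebound, the randomized difference is still 0.21-0.33 D/yr, because it contains loss of effect.

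**Precision of the randomized difference.** Half-width = 1.96 × SD × √(2/n). Per dose, n = 140 × 0.93⁴ ≈ 105 per group at Month 48; pooled, 280 × 0.93⁴ ≈ 209.

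- Per dose: SD 0.50 gives 0.135; 0.55 gives 0.149; 0.60 gives 0.162.
- Pooled: SD 0.50 gives 0.096; 0.60 gives 0.115.
- Wider SD range, per dose: 0.45 gives 0.122; 0.75 gives 0.203. The upper end matters because a one-year rate may vary more than a rate averaged over two or three years.

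These n ignore children on escape by Month 36, who are not re-randomized, so they are somewhat optimistic.

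**Who is in the SAP comparator.** SAP 3.1 and 4.2 keep children already on escape out of re-randomization. The SAP 8.3 comparator is SYD-101 children not re-randomized to Vehicle, which as worded can include them. They qualified for escape by progressing at least 2.00 D, and they could enter the comparator but not the withdrawn group. That breaks the randomized balance. The split by escape use after Month 36 conditions on an event that follows re-randomization.

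**The case against.** A reader might infer that the rebound comparison is uncontrolled, or that ageing could conceal a true rebound altogether. The documents do not support either reading of the SAP. The sentence after the quoted comparison supplies a concurrent group, over the same intervals and by dose, in which ageing would show. The pathway tables give the Month 36-48 rate for continued and withdrawn children at each dose. SAP Section 4 calls for number, mean and SD, so a crude difference could be worked out from them. Absence of a comparator is true only of the rebound paragraph in Protocol 9.4.9, and even that section groups later data by pathway. On masking, the SAP's own rates leave a before/after rise of about 0.09 to 0.20 D/yr with no rebound under 10-20% slowing. Near-cancellation needs much more: with a 0.10 D/yr excess, the rise falls to 0.035 only if the untreated rate has dropped by about 60%.

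It can also be said that the randomized difference does not isolate rebound. That stands. All children initially assigned to Vehicle and not on escape move to 0.03% at Month 36, so no concurrent untreated group exists.

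The analysis is exploratory, and that limits the severity. It does not explain the missing interval, because SAP 8.4 plans pairwise tests and 95% CIs for the quality-of-life items. A side-by-side table gives no effect estimate or uncertainty, and its comparator is not confined to re-randomized children.

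**Conclusion.** The point holds in a limited form. The named rebound analysis is a before/after comparison about two years of age apart. The randomized comparison is only displayed, without a difference or interval, and against a group that may include children who were never re-randomized. The Protocol's rebound paragraph has no comparator.

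Under an assumed 10-20% yearly slowing from 0.65 D/yr, ageing lowers the before/after change by 0.12-0.23 D/yr. The size depends on that assumption; the direction rests on the SAP's own statement about puberty. The result can understate rebound or loss of effect, but the plan does not leave either invisible. Severity is low to moderate, and no primary or secondary endpoint or alpha is touched.

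**What to change.** - Among participants actually re-randomized at Month 36, prespecify the Vehicle-minus-continued difference in SE change and in annual progression rate from Month 36 to Month 48. Report it per dose and pooled, with a 95% CI, adjusted for Month 36 SE and age. Re-randomization is unstratified, so the adjustment is useful.
- Label it the effect of withdrawal, meaning loss of effect plus any rebound. State what would be called rebound and that the design has no concurrent untreated group.
- State how data after escape started post-Month 36 are handled in this estimate, rather than relying on the split by escape use.
- Restrict the SAP comparator to children re-randomized to continue.
- Keep the before/after rates as descriptive support, and align Protocol 9.4.9 with SAP 8.3.

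The cost is one additional model on data already scheduled for collection, plus a short text amendment. It stays exploratory and uses no alpha. SAP 4.2 keeps the re-randomized assignments masked until the Month 48 lock, so specifying the estimate before that lock would be credible.
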